CLE is typically categorized as acute (ACLE), subacute CLE (SCLE), and chronic (CCLE). ACLE develops in nearly one half of patients with SLE, but most or all people with ACLE have SLE. Also known as "malar rash" or "butterfly rash", ACLE is characterized by erythema distributed over the cheeks and nasal bridge of the face.¹ SCLE is less common but may appear as round, scaly lesions with central clearing. Discoid Lupus Erythematosus (DLE), a form of CCLE, is one of the most common forms of cutaneous lupus and can appear as erythematous and hyper- and hypopigmented lesions with telangiectasias. Frequently these lesions lead to scarring and can be permanently disfiguring.

First line management of CLE involves photo protection along with topical corticosteroids and possibly systemic agents. Other treatments include intralesional steroids and/or topical calcineurin inhibitors.¹ Both topical and systemic medications carry a wide range of adverse and toxic effects.³⁻⁵

Though not well-known, laser therapy has been shown to be effective in the treatment of cutaneous lupus.⁶⁻⁸ Many providers may be wary of using lasers on these patients given the ability of ultraviolet light to exacerbate or flare SLE.^{9,10} It is believed that by targeting the superficial vasculature the lasers are able to attenuate the inflammatory response seen in the skin.¹¹

The 585 nm, 595 nm and 1064 nm wavelength lasers have all been shown to be effective in the treatments of cutaneous lupus.^{6-8,12} Given their ability to target vasculature, these lasers are currently used to treat vascular lesions and inflammatory conditions such as port wine stains, telangiectasias, hemangiomas, rosacea, and scars.^{13,14}

Lasers utilizing the 532nm wavelength also have been shown to treat the same vascular and inflammatory conditions as the above mentioned wavelengths. This is due to the fact that the 532nm laser targets the same chromophore of oxyhemoglobin.^{15,16}

Therefore, given that the 532nm has very similar properties and same mechanism of action as other vascular lasers shown to be effective at treating cutaneous lupus it would be reasonable to consider that the 532nm laser could be utilized to treat cutaneous lupus as well.¹⁷

However, since the 532 nm should be used with caution in darker skin people and SLE is 2 to 4 times higher in African-American women than Caucasian women, utilizing only the 532nm would limit the applicability of the proposed study.^{14,18}

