 - Unable to read and speak English since consent will only be available in English

[figure not shown]
- d) Study Endpoints
 - Primary endpoints: Participation in the study will end after the third visit.
 - Primary safety endpoints: none
 - Secondary safety endpoints:
 - Adverse reaction to the laser treatment such as blister, ulceration, and scarring.
 - Adverse reaction to the topical steroid such as atrophy, telangiectasias or striae.
 - Intolerance to pain of laser procedure.

- e) Study Timelines
 - Each participant will be in the study for a maximum of 8 weeks. Participants will receive 2 laser treatments. The laser treatments will be spaced 4 weeks apart between visit 1 and visit 2. Finally, 4 weeks after visit 2, the participants will be followed up during visit 3.

 - The duration expected for all study participants to be recruited is estimated to be 28 weeks.

 - The study will end when the last participant has completed the 2 laser treatments and follow up. The goal is to conclude the data collection by October 31, 2018 and complete primary analysis by December 31, 2018.

- f) Procedures involved in the Human Research.
- This study will be a randomized prospective study. All study lesions will receive topical treatment. One lesion will only receive topical treatment to serve as a control, and up to 2 others will also receive laser treatment in addition to the topical treatment.
 - Standard of care treatment will be a topical corticosteroid as follows:
 - Discoid lupus lesions: Betamethasone dipropionate augmented 0.05% cream twice a day as needed
 - Non-discoid cutaneous lupus lesions: Triamcinolone acetonide 0.1% cream twice a day as needed
 - Laser treatment will be randomized based upon the participant Fitzpatrick Skin Type as follows:
 - Fitzpatrick Skin Types I – III:
 - § Treatment lesion will be treated with 532nm laser or 1064nm laser
 - § 50:50 randomization for laser used (determined by coin flip)
 - § If the participants have an additional lesion then this will be treated with the laser not used for the treatment lesion
 - Fitzpatrick Skin Types IV - VI
 - § Treatment lesion will only be treated with the 1064nm laser. This is because the 532 nm wavelength is absorbed easily by melanin and thus can cause skin pigmentation abnormalities when used with darker skin participants.
 - Laser treatment system details and parameters:

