 - The Excel V laser system manufactured by Cutera (Brisbane, CA) will be used to administer all laser treatments. This laser has the capability of emitting both 532nm and 1064nm wavelengths.
 - Treatments with the 532nm wavelength will utilize parameters in the following ranges:
 - § Spot size: 1-12mm
 - § Fluence: 5-12 J/cm²
 - § Pulse Duration: 3-15ms
 - § Temperature: 5-10°C
 - Treatments with the 1064nm wavelength will utilize parameters in the following ranges:
 - § Spot size: 1-12mm
 - § Fluence: 10-60 J/cm²
 - § Pulse Duration: 10-60ms
 - § Temperature: 5-10°C
 - Note: If the lesions are ill-defined such as those of ACLE and SCLE then a lesion will be defined as a 2cm² within the involved area.

- Timeline:

Pre-Week 0: Screening Visit

- Screening: participant will be screened for inclusion and exclusion criteria, including urine pregnancy test if necessary.

Week 0: Visit 1

- Baseline lesion assessment, lesion selection, randomization and treatment 1 will occur.

Week 4: Visit 2

- Follow up lesion assessment
- Treatment 2

Week 8: Visit 3

- Final lesion assessment

- Lesion assessment:

Limited CLASI:

The classification of cutaneous lupus will be recorded for each participant.

A “limited” CLASI scoring system will be used, subdivided into an “active” and “damage” components.

The limited active CLASI for a lesion will include the following:

- Erythema (ranging from 0 = absent to 3 = dark red/purple)
- Scale/Hypertrophy (ranging from 0 = absent to 2 = verrucous/ hypertrophic)
- The addition of these scores result in a total limited active CLASI score of the studied lesion, ranging from 0 to 5.

The limited damage CLASI for a lesion will include the following:

- Dyspigmentation (0 = absent or 1 = present)
- Scarring/Atrophy/Panniculitis (ranging from 0 = absent to 2 = severely atrophic scarring or panniculitis).
- The addition of these scores result in a maximum damage score of 3.

The total limited CLASI reflects the sum of both active and damage CLASI, resulting in a score ranging from 0 to 8.

Photographs will be taken of all study lesions during every assessment.

All participants will be evaluated by [name] at baseline and at subsequent visits.

All participants will be evaluated via photograph by [name] at baseline and subsequent visits. [name] will be blinded to the treatment type so as to be an independent observer. He will utilize the “Independent Observer Survey” to document his assessments.

Visual Satisfaction of Appearance:

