In addition participants will rate the cosmetic results on a visual analog scale (VAS).

A score of 0 will represent a cosmetically fully unsatisfactory result and 10 will represent cosmetically excellent result.

- Adverse Effects:

Pain: After each treatment pain will be recorded on VAS. A score of 0 will represent absence of pain and 10 will represent maximal pain.

Other adverse effects that will be monitored for:

- Hyperpigmentation
 - Hypopigmentation
 - Crusting
 - Vesiculation
 - Scarring
- Risk Management:
Participants will be directly observed for any adverse effects during treatment. The chances of a research related injury are extremely rare. However treatment for research related minor injuries will be made available at no cost by [name] if possible. For injuries that cannot be treated by [name] the participant will be referred elsewhere. Costs associated with this treatment may be billed to the participant's insurance company. Costs not covered by participant's insurance company will be the participant's responsibility.

Participants will not be misled in anyway about procedures/activities being performed

Research will be conducted during [name] clinical time.

The duration of research should take approximately 12 months. The research study will begin recruitment directly after IRB approval in hopes of being finished by December of 2018.

No audio or video recordings will be used in this study. However photographs will be taken of the lesions for assessment purposes. Though the photos will not contain any identifiers, participants are potentially identifiable from the photos and thus they will be stored in the HIPAA-compliant electronic health record (EHR) of UCF Health.

A study survey document (see attached "Survey" and "Independent Observer Survey") will be used to record the following:

- Age
- Gender
- Pregnancy Status
- Fitzpatrick Skin Type
- Past Medical History
- Medications
- Allergies
- Lesion locations
- Lesion type
- Lesion treatment
- Limited CLASI
- Patient cosmetic assessment

- Whether patient would recommend treatment
- Pain and adverse effect assessment

Note: the above information will be collected from the medical records and during the study visits.

Medical records in the HIPAA-compliant EHR at UCF Health will be used to obtain the following data:

- Age
- Gender
- Past Medical History
- Medications
- Medication Allergies
- Social History
- Photographs
- Laboratory Results

Student/school records are not to be used.

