g) Data and specimen management

There will be no specimen collection, and thus there will be no management of physical specimens.

If a participant withdraws from the study, the reason for the withdrawal will be noted but data collected up to that point will be used.

All data will be collected on the survey documents (see attached documents “Survey” and “Independent Observer Survey”). These survey documents will be stored in regulatory binder in a locked drawer in locked room at UCF Health. This will only be accessible only to the principal investigator and co-principal investigators. These survey documents will then be used to transfer the data to the REDCap database, afterwards they will be disposed of in HIPAA-compliant shred bin.

Photographs of study lesions will be stored directly in the EHR.

The data will be analyzed for significant differences with aid of a statistician. A significance level of 0.05 will be used for statistical hypothesis testing. The results of the data analysis will be graphed for each parameter.

h) Provisions to monitor the data for the safety of participants

The principal investigator and statistician will periodically review cumulative CLASI scores and adverse effect data every 10 patients.

If the change in the active CLASI score for the treatment lesion is 3 points higher than the change in the active CLASI score for control lesions with $p < 0.05$ then the study will be suspended immediately.

If participants have ulceration or scarring attributable to the laser treatment as an adverse effect with $p < 0.05$ then the study will be suspended immediately.

i) Withdrawal of participants

Participants will be withdrawn from the research without their consent if they become intolerant to the laser treatments and/or the investigators determine that they are too nervous, anxious to continue.

Participants may terminate their participation in the research study at any time by informing a member of the research team. If the participant declines any further laser treatments he or she may still participate in the study with follow up assessments being completed.

If participants miss study Visit 2, the researchers will attempt to reach the participant to reschedule. If the participant is unable to reschedule within 2 weeks of the missed appointment then the participant will forego the 2nd treatment and attempted to be scheduled for Visit 3.

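### Four of the seven safety outcomes in section 7 d) are absent from the monitored list in 7 f); three of them, including the suspension trigger ulceration, have no named assessment item in the visible protocol text

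*Combined protocol and SAP*

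**What the plan says.** Section 7 d) (Study Endpoints) sets out three kinds of safety outcome, all secondary. For the laser it gives "Adverse reaction to the laser treatment such as blister, ulceration, and scarring". For the corticosteroid cream the entry reads "Adverse reaction to the topical steroid such as atrophy, telangiectasias or striae". The third entry concerns tolerability and reads "Intolerance to pain of laser procedure".

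Section 7 f) (Adverse Effects) says "After each treatment pain will be recorded on VAS". Under "Other adverse effects that will be monitored for" it then lists five effects: hyperpigmentation, hypopigmentation, crusting, vesiculation and scarring.

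Section 7 f) (Lesion assessment) scores each study lesion on a limited CLASI. The damage part has a yes/no dyspigmentation item and a combined item, "Scarring/Atrophy/Panniculitis (ranging from 0 = absent to 2 = severely atrophic scarring or panniculitis". The timeline places lesion assessments at Weeks 0, 4 and 8, and all study lesions are photographed each time.

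Section 7 h) has the principal investigator and the statistician review CLASI scores and adverse-effect data after every 10 patients. One suspension rule begins "If participants have ulceration or scarring attributable to the laser treatment as an adverse effect" and adds the condition p < 0.05.

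**The concern.** The endpoint list, the monitoring list and the suspension rule should name the same events, and they do not. An event that is an endpoint in 7 d) and a trigger in 7 h), but is not an item in 7 f), depends on someone noticing it and volunteering it. If it is not asked about at each visit, a count of zero in the report cannot safely be read as no occurrence. The ulceration half of the 7 h) rule would then rest on a data source that the protocol does not define.

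The steroid endpoints are affected most: none of the three is on the monitored list. Telangiectasias carry a further difficulty. Section 4 (Background) says that discoid lesions "can appear as erythematous and hyper- and hypopigmented lesions with telangiectasias", so a telangiectasia seen at Week 8 may be disease that was there at the start. No baseline item is named that would tell the two apart.

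**Working it through.** The protocol states no figure on this point, so the check is a comparison of lists.

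**Step 1: count the outcomes in 7 d).** Laser 3 + steroid 3 + pain 1 = 7.

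**Step 2: match them to the monitored list and the pain VAS, then to the limited CLASI.** Blister is taken as equivalent to vesiculation, and pain intolerance as covered by the VAS.

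| Outcome in 7 d) | Monitored list or VAS in 7 f) | Limited damage CLASI |
|---|---|---|
| Blister | Yes, as vesiculation | No |
| Ulceration | No | No |
| Scarring | Yes | Yes, combined item |
| Atrophy | No | Yes, combined item |
| Telangiectasias | No | No |
| Striae | No | No |
| Intolerance to laser pain | Yes, by VAS | No |

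On the monitored list or VAS: 3. Absent: 7 − 3 = 4 (ulceration, atrophy, telangiectasias, striae). Crediting the CLASI with atrophy leaves 4 − 1 = 3 with no named item (ulceration, telangiectasias, striae). Strict word-for-word matching would leave 6 of 7 unmatched, since only scarring appears identically in both places; that reading is too strict and is not used.

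**Step 3: ask what the combined CLASI item can show.** It pools scarring, atrophy and panniculitis on a 0 to 2 scale. A rise does not say which of the three caused it, and a lesion already at 2 at baseline cannot score worse. It therefore collects atrophy without isolating steroid atrophy.

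**Step 4: compare with 7 h).** The adverse-effect suspension rule names two events. Scarring is on the monitored list and in the CLASI. Ulceration is in neither; it appears only as an endpoint and as a trigger.

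**Step 5: look for other routes in the text.**
- The direct observation described under Risk Management in 7 f) is confined to the treatment session, so it would not pick up an ulcer or striae that develop between visits.
- Photographs are taken at every assessment, but nothing says they will be read for these effects.
- The Survey has a general entry for pain and adverse effects. Its content is in an attachment, and the only specific adverse-effect content in the protocol text is the 7 f) list.
- Under 7 g), the paper surveys are destroyed once transferred to the database, so an item that was never asked could later be sought only in photographs or other clinic records.

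**The case against.** The strongest reply is that a difference between two lists does not prove that data go uncollected. The examples in 7 d) follow the words such as, and the 7 f) list is not said to be exhaustive. Participants are evaluated in person at baseline and later visits, a blinded observer assesses photographs, and adverse-effect data are reviewed every 10 patients. Naming ulceration as an endpoint and a trigger is itself a commitment to look for it. The Survey may already carry every item.

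Most of this stands, and it limits the point. A reader might infer that the plan does not collect the four outcomes. The documents do not support that: atrophy is scored within the CLASI, and the Survey could not be seen.

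A reader might also infer that harms in general cannot be separated from existing lupus damage. That goes too far as well. Dyspigmentation and scarring are scored per lesion at baseline, and each participant has a control lesion that receives topical treatment only. The baseline difficulty is real for telangiectasias, which have a baseline photograph but no scored item, and for steroid atrophy, which is pooled with disease scarring.

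Nor do the risk percentages in section 8 measure what would be lost. They are upper limits; the category below 1% for wounds does not name ulceration, and it includes blistering, which the monitored list covers as vesiculation.

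What the reply does not remove is that none of these routes tells staff to ask about ulceration, telangiectasias or striae at each visit.

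**Conclusion.** The point holds as a gap in specification. Four of the seven safety outcomes are absent from the monitored list. One of these, atrophy, is scored only in a combined item. Three (ulceration, telangiectasias, striae) have no named assessment item in the visible text, and ulceration is one of the two adverse-effect events that can suspend the study. Systematic collection of these outcomes is not assured.

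This is more than missing detail: staff who follow the stated list exactly would leave a suspension trigger and two steroid endpoints without a defined record.

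The conclusion rests on treating blister as vesiculation and pain intolerance as covered by the VAS, and on the protocol text alone. If the Survey already lists the items, the remaining fault is that 7 d), 7 f) and 7 h) disagree. No number of missed events can be derived from the documents.

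**What to change.** Reconcile 7 d), 7 f) and 7 h):

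- Add ulceration, atrophy, telangiectasias and striae to the monitored list in 7 f), and to the Survey if they are not already there.
- Record each as its own item for every study lesion, including the control lesion, before treatment at Visit 1 and again at Visits 2 and 3. Atrophy should be recorded separately from the combined CLASI item.
- Report items that are new or worse since baseline, beside the same participant's control lesion.
- State that these lesion-level counts are the adverse-effect data reviewed under 7 h).

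The cost is a few extra form items per lesion at visits already planned, with no new visit or procedure.

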Study of the Efficacy of 532nm Laser and 1064 nm Laser in the Treatment of
Cutaneous Lupus Erythematosus Versus Topical Corticosteroids Alone

NCT03639857

Date: May 22nd, 2019

1) Protocol Title

A Comparative Study of the Efficacy of 532nm Laser and 1064 nm laser as Adjuncts to Topical Corticosteroids in the Treatment of Cutaneous Lupus Erythematosus Versus Topical Corticosteroids Alone

2) Principal Investigator

[name] M.D., UCF College of Medicine, UCF Health

Co-Principal Investigator: [name] M.D., UCF Health

Co-Principal Investigator: [name] B.S., UCF College of Medicine

Co-Principal Investigator: [name] B.A., UCF College of Medicine

Co-Principal Investigator: [name], B.S., UCF College of Medicine

Co-Principal Investigator: [name], B.S., UCF College of Medicine

Sub-Investigator: [name], B.A., UCF College of Medicine

Sub-Investigator: [name], B.A., UCF College of Medicine

3) Objectives

This study aims to compare the efficacy of 532nm Potassium Titanyl Phosphate (KTP) laser and 1064 nm Neodymium-doped Yttrium Aluminum Garnet (Nd:YAG) laser as adjuncts to topical corticosteroids in the treatment of cutaneous lupus erythematosus versus topical corticosteroids alone.

Our hypothesis is that adding laser treatment to standard of care will result in quicker resolution of lesions of cutaneous lupus. Furthermore we hypothesize that the 532nm laser will be more effective than the 1064nm laser.

The results of the study will either be submitted for publication in a journal or presented at a conference. Data from this study also could be used for further studies to clarify the ideal laser settings for use in cutaneous lupus.

4) Background

Systemic Lupus Erythematosus (SLE) is an autoimmune disorder characterized by the production of autoantibodies that can affect almost every organ in the human body. Most commonly there is a skin and musculoskeletal involvement, but there also can be hematologic, renal, and central nervous system manifestations as well.¹

It is estimated that 80% of people with SLE have skin involvement referred to as Cutaneous Lupus Erythematosus (CLE). CLE can develop independently of SLE and is more prevalent than SLE alone. Women ages 20 to 50 years old are most commonly affected by CLE although males and other ages can be affected as well.²

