Therefore, we are proposing investigating the use a 1064nm laser as well in treating cutaneous lupus as this wavelength is safe on people of all skin types.⁹ The 1064nm laser has previously been shown to be effective in cutaneous lupus though further studies are needed to confirm the preliminary findings and better characterize the effectiveness.¹¹

When compared to available topical and systemic therapies, laser therapy generally has been shown to have minimal side effects. The most common adverse effect is bruising

but that usually clears within 10 days. Other adverse effects include temporary dyspigmentation and very rarely scarring, vesiculation, and crusting that usually fade within a few weeks.¹⁴

The 532nm laser and 1064nm wavelength lasers are currently being used in an off-label manner by [name] of UCF Health to treat patients with cutaneous lupus with excellent clinical results. As there is limited data on the use of the 532nm and 1064nm lasers for cutaneous lupus, we hope to quantify the magnitude of the results in a prospective manner.

As lasers with these wavelengths are present in many dermatology practices, we hope that data from this study will educate and encourage more providers to use lasers, such as the one in this study, to benefit their patients with cutaneous lupus.

5) Setting of the Human Research

- The human research will be conducted at UCF Health Clinic at [name].
- UCF College of Medicine's resources will be used during data analysis
- We have obtained permission and approval from UCF Health medical director [name]

6) Resources available to conduct the Human Research

- Participants will be recruited through the UCF Health Clinic, Lupus Foundation of Florida, and the Central Florida Society of Dermatology. This represents a large pool of potential participants from which to recruit.
- The study's small sample size (N=25) makes it likely that the required number of participants will be recruited in less than 12 months.

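### On its natural reading, the active-CLASI suspension rule pools the two lasers, so severe worsening confined to 532nm would rarely suspend the study

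*Combined protocol and SAP*

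**What the plan says.** Section 7(h) has the principal investigator and statistician "periodically review cumulative CLASI scores and adverse effect data every 10 patients". With 25 participants planned, that means reviews at 10 and 20. The activity trigger is met if "the change in the active CLASI score for the treatment lesion is 3 points higher than the change" on control lesions with p<0.05, and the study is then suspended at once. A second trigger covers ulceration or scarring and is not at issue here.

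Section 7(f) sets what the treatment lesion receives. In Fitzpatrick types I–III a coin flip chooses 532nm or 1064nm. In types IV–VI, "Treatment lesion will only be treated with the 1064nm laser". For types I–III it adds: "If the participants have an additional lesion then this will be treated with the laser not used for the treatment lesion".

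The lesion assessment text in 7(f) defines a "total limited active CLASI score of the studied lesion, ranging from 0 to 5", with higher scores meaning more erythema and scale. Section 8 lists worsening of cutaneous lupus among the laser risks.

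**The concern.** One label, the treatment lesion, covers two different interventions, and 7(h) sets no criterion for either alone. If only the 532nm lesions worsened, the 1064nm lesions would pull the average gap towards zero and the 3-point threshold would be hard to reach. This is the only stated suspension trigger based on lupus activity.

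The plan does not treat the two wavelengths as interchangeable. Section 3 states "we hypothesize that the 532nm laser will be more effective than the 1064nm laser", and 7(f) withholds 532nm from darker skin because of pigment effects.

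Two details add to the difficulty. Read literally, the rule leaves out the additional lesion, which gets the other laser. The sign of change is also undefined, although the safety heading and the direction of the scale point to worsening.

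**Working it through.** The plan gives no operating characteristics for this rule, so there is no figure to reproduce.

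**Inputs from the protocol.** Threshold 3 points and p<0.05 (7h); reviews at 10 and 20 participants (7h); active score 0–5 (7f); coin-flip probability 0.5 in types I–III and 1064nm only in types IV–VI (7f).

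**Assumed, because the protocol gives none.** SD of the gap (laser lesion minus control lesion), skin-type mix, share of participants with an additional lesion, baseline scores, and a two-sided paired t test.

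**Step 1, dilution.** If q is the share of types I–III, the expected 532nm share of treatment lesions is p = 0.5 × q, at most 0.5. The expected pooled gap is p × (532nm gap) + (1 − p) × (1064nm gap). With 1064nm equal to control and p = 0.5, a pooled gap of 3 needs a 532nm gap of 3 / 0.5 = 6, and a 532nm gap of 5 gives 2.5. With half the participants in types IV–VI, p = 0.25, and a gap of 4 gives 1.0.

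**Step 2, chance imbalance in the coin flip.** Ignore other variation and let x of the first 10 treatment lesions be 532nm.
- 5-point harm: 5x/10 ≥ 3 needs x ≥ 6. The probability is 0.377, 0.145, 0.063 or 0 with 10, 8, 7 or 5 participants in types I–III.
- 4-point harm: 4x/10 ≥ 3 needs x ≥ 8. The probability is 0.055 with all in types I–III.
- At 20 participants, 5-point harm needs x ≥ 12. The probability is 0.252 with all in types I–III.

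**Step 3, simulation at the first review.** n = 10; gaps are normal, rounded to whole points and limited to −5 to 5; harm is on 532nm only. The rule fires if the mean gap is at least 3 and p<0.05. Ranges run from no additional lesions to one in every type I–III participant.

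| Skin types | Harm, SD | As written | With wavelength checks |
|---|---|---|---|
| All I–III | 3 points, SD 1 | 0.5% | 55–57% |
| All I–III | 4 points, SD 1 | 8% | 94–99.9% |
| All I–III | 4 points, SD 2 | 7% | 76–91% |
| Half IV–VI | 3 points, SD 1 | 0% | 34–58% |
| Half IV–VI | 4 points, SD 1 | 0% | 55–99% |
| Half IV–VI | 4 points, SD 2 | 0.1% | 37–84% |

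At n = 20, SD 1 and 4 points, the rule as written fires in 2% (all I–III) or 0% (half IV–VI).

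**Step 4, the cap on scores.** Step 3 bounds the gap but not the scores themselves. A lesion starting at 3 can rise by only 2 points, so a 3-point gap also needs its control lesion to improve. The checks were re-run with whole-number scores bounded 0–5, gap SD about 1 and a mean drift of −0.5 on both lesions (n = 10, both skin mixes). They fire as follows:

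| Baseline active score | Nominal 3 points | Nominal 4 points |
|---|---|---|
| 1–2 | about 30–55% | about 50–99% |
| 1–3 | about 25–35% | about 40–80% |
| 2–4 | about 2–10% | about 8–20% |

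The right-hand column of Step 3 therefore describes mild baselines only. In a separate bounded model (baseline 1–3, nominal harm 3–5 points), the rule as written fired in 0–7% by the second review.

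**Step 5, harm on 1064nm only.** In the Step 3 model with 4 points and SD 1, the rule as written fires in 8% (all I–III) and 50% (half IV–VI). If all participants are types IV–VI there is no dilution, and a 4-point harm fires it essentially always.

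**Step 6, few lesions.** A mean gap of 3 on m lesions reaches p = 0.05 only if the SD is at most 3√m / t(0.975, m − 1). That is 1.21 for m = 3 and 1.89 for m = 4. Without additional lesions, the chance of fewer than three 532nm lesions at n = 10 is 5%, 14% or 50% with 10, 8 or 5 participants in types I–III.

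**The case against.** **Pooling is a reading.** The rule does not say that it averages over lasers, and lesion treatment and limited CLASI are recorded, so the reviewers could look by wavelength. Near-maximal worsening would probably be seen at visits or on photographs. All of that is fair, but no text requires a look by laser or prescribes action if one is bad. Averaging in the additional lesions does not help either: if every participant has one, 532nm is fixed at 50% and even a 5-point harm averages 2.5.

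**The scenario is extreme.** It needs a mean excess of about 3 points or more on one laser with the other near control. If 1064nm also worsens by 1 or 2 points, a 4-point 532nm harm fires the rule as written in 19% or 52% (all I–III), or 0.3% or 11% (half IV–VI). This stands and limits the point's importance.

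**The margin may matter more than the pooling.** At baseline 2–4 the added checks would also rarely fire. This stands too.

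**Stronger readings a reader might infer.** One is that harm from either laser would go undetected; Step 5 shows that this is too broad. Another is that 532nm is the riskier or less tested laser. Section 4 says both are "currently being used in an off-label manner" for cutaneous lupus at this clinic and calls the 1064nm findings preliminary. The documents describe no 532nm-specific route to a lupus flare, and the hypothesis in section 3 concerns relative efficacy, not harm.

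**Conclusion.** The point holds for 532nm. With 532nm expected on at most half of treatment lesions, and on fewer with each type IV–VI participant, a 3–4 point excess confined to it would suspend the study in about 0–8% of first reviews. This assumes the pooled reading, 1064nm equal to control, SD 1 and a paired t test; SD 2 gives a similar figure at 4 points. Harm on 1064nm alone is diluted less, and hardly at all when most participants are types IV–VI.

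It would be wrong to conclude that the rule cannot fire. A 5-point 532nm harm with every participant in types I–III reaches it in roughly a third of trials by the second review (35–37% in a model that does not cap scores). It would also be wrong to expect wavelength checks to cure the problem: their gain is substantial at low baseline activity and small at baseline 2–4. The change is worth making as a modest safety improvement.

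**What to change.** In 7(h):
- Define change as follow-up minus baseline active score (positive means worse), and the gap as the laser lesion's change minus that of the same participant's control lesion.
- Keep the overall check.
- Add the same check (mean gap of at least 3 points, p<0.05) for all 532nm lesions and for all 1064nm lesions, counting treatment and additional lesions. If either is met, suspend that wavelength or the study.

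Each participant contributes at most one lesion per wavelength, so a paired test remains valid.

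The cost is a few lines of protocol text and one more table at reviews already planned, from data already recorded. The chance of a precautionary pause when there is no harm rises slightly: 0% at SD 1, at most 0.06% at SD 1.5 and at most about 0.3% at SD 2. With many type IV–VI participants, the first review may hold too few 532nm lesions for the check to work, which is one reason to keep the overall check. Whether to lower the 3-point margin is a separate clinical judgement for the investigator and the IRB.
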